4.0 Eligibility Criteria

Inclusion criteria:

1. Overtly healthy men and women aged 21 – 35
2. Able to give informed consent
3. Able to understand/complete questionnaires and procedures in English
4. Willing and able to adhere to the study schedule
5. At least 2 binge drinking events (at least 4 or 5 drinks on a drinking day for women and men respectively over the last 5 weeks, unless determined by study physicians that drinking history meets study objectives
6. Have venous access sufficient to allow blood sampling

Exclusion criteria:

1. Pregnant or breast-feeding
2. Desire to be treated for any substance use disorder or court ordered to not drink alcohol
3. Medical disorders or other conditions, such as lifetime history of a seizure, including history of ECT but excluding febrile seizures and those induced by substance withdrawal, that may influence study outcome or subject safety
4. First degree relative with idiopathic epilepsy or other seizure disorder
5. DSM 5 Disorders (non-AUD) or current/history of neurological disease of cerebral origin, or head injury with > 20 min loss of consciousness, if determined by the study physicians to affect subject safety or data integrity

6. Positive urine drug screen for amphetamines/ methamphetamines, barbiturates, benzodiazepines, cocaine, opiates, or phencyclidine if determined by the study physicians to adversely affect subject safety or data integrity
7. Medications (past 30 days) that could influence subject data/subject safety (e.g. antidepressants, antipsychotics, benzodiazepines, etc.) as determined by study physicians
8. Positive BrAC reading at beginning of any study session
9. Actively suicidal (for example, any suicide attempts within the past 3 months or any current suicidal intent, including a plan) or are at serious suicidal risk, by clinical judgment of the study physicians
10. Any condition for which the study physicians determine it is unsafe or not prudent to enroll a subject

5.0 Study Design

This will be a single site randomized, 2-session, within-subject cross-over design pilot study (Figure 2). 20 enrolled (of 30 consented) subjects reporting varying levels of binge and high intensity drinking, defined as at least 2 episodes of drinking 4 (for women) or 5 (for men) drinks on an occasion over the last 5 weeks, (unless determined by PI that drinking history meets study objectives), will be enrolled. Subjects will be randomized to undergo one session of rTMS or sham immediately followed by our rate control IV ASA paradigm. Subjects will then return 7-14 days later and undergo the same sequence of events with the opposite intervention (i.e. rTMS or sham) from session 1.

Duration of Treatment

Subjects will complete two stimulation (LF and sham) and IV ASA paradigm sessions over two to three weeks, with one session occurring every 7-14 days. Previous work has demonstrated that a single session of rTMS is sufficient to modulate AUD related behavior³⁰.

Clinical Research Sites

rTMS treatments and alcohol challenge sessions and lab visits will take place at the Indiana Clinical Research Center, in either Goodman Hall at the Neuroscience Center and/or in the Neural Systems Laboratory at Indiana University Hospital.

[name] is the Medical Director of the IU Neurostimulation Program and is a psychiatrist in the IU Department of Psychiatry. [name] and associated research personnel will conduct TMS procedures, help with subject transportation and monitoring, and assist with gathering demographic data. The program has 1 research psychiatrist and 1 research coordinator.

[figure not shown]

Figure 2: Study Design for rTMS Modulation of ASA

[name] is the Research Medical Director of the IU Psychotic Disorders Program (IUPDP). The IUPDP is located in Indianapolis, IN. and is part of the IU Department of Psychiatry. IUPDP research personnel will conduct TMS procedures, help with subject transportation and monitoring, and assist with gathering demographic data. The IUPDP has 2 research psychiatrists, a fully dedicated study manager, a fully dedicated study coordinator, one dedicated subject recruiter, and two raters (1 PhD, 1 Masters level) who have been trained and have extensive experience in conducting the assessments and cognitive tests used as outcome measures.

6.0 Enrollment/Randomization

Subjects will be recruited through the NSL registry, and self-referrals through advertisement and word-of-mouth. Subjects that meet inclusion/exclusion criteria will be enrolled at the discretion of the Principle investigator and randomly assigned to one of the two schedules (rTMS first, or Sham first).

7.0 Study Procedures

Recruitment and Screening

Subjects from the NSL registry will be contacted by phone or email, while other subjects will contact the study phone line or email after learning about the study from print, electronic advertising, or word of mouth. Subjects who meet basic criteria will either 1) be invited for an in-person interview when they will consent to participate in the study, or 2) arrange for a remote interview where they will consent to participate and complete interview measures electronically and converse with study staff via IU Zoom Health or similar secure platform. Subjects will complete some or all of the following measures, at the discretion of the principal investigators:

Self-Report Measures:

- The Alcohol Use Disorders Identification Test (AUDIT)
- The Family History of Alcoholism Module of the SSAGA
- The UPPS-P Impulsive Behaviors Scale measures impulsivity traits
- Self-Rating of Effect of Alcohol assessing retrospective sensitivity to the subjective response to alcohol (SRE).
- Short Inventory of Problems – Revised (SIP-r)
- Medical History (including menstrual phase for women)

- Nicotine History Measure
- Penn Alcohol Craving Scale (PACS)
- Subjective Response Questions
- Five Factor Model Form
- Drinking Refusal Self-Efficacy Questionnaire-Revised (DRSEQ-R)
- Alcohol Expectancy Questionnaire (Full and Brief versions)
- Drinking Motives Questionnaire (Full and Brief versions)
- COVID-19 Questionnaire

Interviews:

- The Semi-structured Assessment for the Genetics of Alcoholism – II, Alcohol

Diary Measures:

- Timeline Follow-back (TLFB) modified to assess for one-month recall of alcohol, tobacco, drug, and cannabis use

Screening tools:

- Clinical Institute Withdrawal Assessment for Alcohol Scale (CIWA)
- GAD-7 and GAD-2 Generalized Anxiety Disorder Assessment, 7 and 2 item scales assessing anxiety symptoms over the last 2 weeks
- PHQ-9 and PHQ-2 Patient Health Questionnaire, 9 and 2 item scales assessing depressive symptoms over the last 2 weeks
- Urine pregnancy and drug screen (UPS, UDS, including EtG urine screen at discretion of study physicians)
- Breath Alcohol Concentration Measurement
- Liver function assessment
- TMS Screening Checklist

Miscellaneous:

- Contact Form and Follow-up questionnaires

Note: Screening tool score above the cutoff or concerning patterns as determined by the study technician may prompt additional testing from the set of measures completed at the interview (For example, PHQ-2 score greater than or equal to the cutoff of 3 will prompt completion of the PHQ-9.).

Subjects that complete part of the interview remotely and appear to meet study criteria will be asked to visit the ICRC for a short visit where they will provide a blood sample, urine, and be paid the interview fee of \$25. Blood samples may be stored indefinitely in a secure location for future genetic research. There is not a plan to submit to the NIH genomic database. At this time, there is no planned analysis for these samples and due to our sample size, we do not meet the requirements for inclusion in the NIH genomic database. Subjects who complete part of the interview remotely and do not meet study criteria will be informed of the decision and mailed a check or gift card in the amount of \$25.

Based on the information collected at the screening interview, the investigators will decide whether or not to enroll the subject in the study. If the subject is enrolled in the

study, they will be either randomly assigned to one of the two schedules, or assigned to one of the two schedules based on group enrollment balance or subject safety at the discretion of the study physicians, and contacted to schedule their experimental sessions. If the subject agrees to enroll in the study and schedules their study visits, they will be sent an email with pertinent information.

Procedures on the testing day

Orientation to Laboratory: On the days of testing, the subject will arrive at the ICRC between 7:00 and 9:00 am and undergo a brief physical exam by ICRC Nurses, testing of urine for hCG in females and a drug screen for all subjects, and documentation of zero BrAC before a 550 cal breakfast is served. *Study protocol will be reviewed and car keys, if the subject drove themselves, taken for safekeeping or confirmed that the keys are held by the hospital valet service.* Age, sex, blood pressure, heart rate, temperature, height, and weight will be measured.

rTMS Treatment

Immediately before rTMS administration, subjects will be prompted to recall their most recent experience using alcohol through a standardized series of cue-induced questions. During the rTMS/sham sessions, subjects will be instructed to imagine themselves in that scenario. These mental priming techniques have been previously employed by study collaborator [name].

rTMS will be delivered using the Magventure MagPro X100 Magnetic Stimulator (Magventure Inc., Alpharetta, Georgia). Motor threshold (MT) will be determined using single pulse stimulation over the left primary motor cortex, assessed as the lowest intensity producing five visible movements of the right abductor pollicis brevis out of ten stimulations. The Magventure MagPro X100 is equipped with a research-dedicated coil with combined active and sham stimulation capabilities, with both functions sharing the same acoustic properties. The sham condition additionally mimics cutaneous stimulation, facilitating subject blinding. Study conditions (1 Hz, sham) will be assigned a label, such as A or B, by a non-blinded staff member who is not directly involved with the research team. Subjects will be assigned a sequence of blinded study conditions in randomized and counterbalanced fashion.

The rTMS coil is held in place by a movable arm attached to the chair in which the subject sits. The coil is placed, by the PI, over the intended target and rests gently on the subject's head. The movable arm is then locked in place by the PI, who is present during the entire stimulation session to assess for subject comfort.

Low frequency rTMS: Low frequency rTMS, or rTMS at 1 Hz or less, is able to produce an inhibitory effect on local brain activity. This has been observed in healthy subject motor corticospinal output⁴⁰. Previous studies have demonstrated that a single session of 1 Hz rTMS is capable of inhibiting local brain activity and modulating distal but related circuitry³³. This work is in-line with the use of 1 Hz stimulation proposed in this study.

Low Frequency rTMS Protocol: Subjects will receive one session of low frequency rTMS

targeting the mPFC, delivered over FP1 per the 10-20 international scalp electrode location system (an approach taken by our consultant^{41,42}), within the following stimulation parameters: Continuous 20-minute train of 1 Hz rTMS, at 110% of MT, for a total of 1200 pulses. This protocol was shown by Chen et al. (2013) to produce an inhibitory effect on local cortical excitability as well as effects on connectivity of related circuitry³³. The stimulation design is within safety limits for rTMS^{32,40,43}. If needed for tolerability, stimulation intensity (% MT) may be decreased, down to but not beyond the subjects resting MT, during the course of the study section.

rTMS administration monitoring

All subjects will be instructed to wear earplugs during each rTMS session and will be monitored by medically trained research staff throughout the entirety of each rTMS session.

Subjects will complete the rate control IV alcohol self-administration session as soon as feasible after rTMS administration. Upon completion of the alcohol self-administration session, subjects be taken to the ICRC for post-session monitoring until the time for discharge.

Alcohol Administration

Laboratory Testing: Each subject will be tested during each of two outpatient visits spanning Goodman Hall and University Hospital. After testing is complete, subjects will remain at the ICRC until at least 7 pm or their BrAC reaches 35 mg/dL, whichever is later.

Preparation for Testing: Using sterile technique, a 20 gauge (or 22 gauge if necessary) indwelling venous catheter will be placed in an antecubital vein by an ICRC nurse, then flushed with saline and capped with a heparin lock. The subject will be instructed in the use of the Draeger® BrAC meter and familiarized with the subjective response procedures under NSL technician supervision.

Preparation for Infusion: After the subject is prompted for a bathroom break, the venous catheter will be Y-connected to 2 parallel infusion pumps, each capable of delivering up to 999 ml/hr and set to deliver 4 ml/hr to keep the vein open. Subject concerns of any kind will be addressed, and the start of the infusion, marking the beginning of experimental time, $T_{xp} = 0$, will be announced. Subjects will be unaware of BrAC readings and infusion rates at all times. The subject will be able to talk to the technician at any time without manual effort.

Infusion rate profile computation:

Using individualized PBPK parameters⁴⁴, the Computer-assisted Alcohol Infusion Software⁴⁵⁻⁴⁸ will deliver an approximately 6.0 % (v/v) alcohol solution prepared by the Research Pharmacy. The infusion rate profile is based on individualized physiologically-based pharmacokinetic model parameters to achieve specified incremental alcohol exposure rates independent of the subject's age, height weight and gender. The safety limit will be set to 170 mg/dL, but subject inputs that would exceed 165 mg/dL are

disabled, allowing subjects to self-administer to a high-intensity drinking threshold of 160 mg/dL if they so choose and accommodating potential deviance from our pharmacokinetic modelling or measurement error.

We will use the rate control paradigm during the 90-minute alcohol self-administration session to allow the subject to determine their alcohol exposure trajectory (Figure 3). For the first self-administration epoch and at the end of each subsequent 3-5 min self-administration interval, the subject will specify the next alcohol exposure rate. Alcohol delivery raises the subject's BrAC by the specified rate over 3-5 minutes. During the last ~0.5 minutes of the exposure, the subject may complete the brief computer-assisted assay of craving for alcohol and subjective response and then select the next exposure rate, all while the current exposure rate is maintained.

[figure not shown]

Figure 3: Exposure Rate Selection and Subjective Response Determination Sequence. The task begins with an initial exposure rate selection, with the display indicating no past rate of change (baseline). After 2.5 minutes, a set of subjective responses are collected over approximately 20 sec after which time the next exposure rate selection prompt is displayed, now indicating the prior selection in the left hand (shaded) portion of the display. The choice and subjective response sequence is repeated throughout the experiment. The next exposure rate is then selected by rotation of the CAIS response button (Griffin Technologies Powermate®, inset) to a position within the available range depicted in gray. The arrow position follows button rotation in real time, and rate chosen by single button press. Text instructions are for illustrative purposes.

Subjects approaching the functional exposure limit of 165 mg/dL will have their range of BrAC choices limited in a corresponding way. An alcohol self-administration session may be terminated early at the discretion of the study investigators if the outcome measures have been obtained (for example, the safety limit has been reached and thus binge and high intensity drinking alcohol exposures achieved with corresponding subjective responses). Subject payment will not change and they will not be informed of the reason for early termination to preclude change in behavior at any subsequent sessions.

Except for *ad-libitum* bathroom breaks, participants remain in the testing environment for the duration of the experiment; technician interaction is limited to occasional BrAC samples and dependent-measure data collection.

Upon completion of the infusion and return to the ICRC, participants are served a meal from the ICRC kitchen and remain in a room until at least 7:00 pm, or until BrAC < 35 mg/dL. Subjects may discharge earlier at the discretion of the principal investigator and if transportation has been arranged for them, however subjects are not informed of this

option as it is exercised only in emergencies or urgent situations. If the BrAC is 40 mg/dL or higher at 5:30pm, the participant will be offered a dinner from the ICRC kitchen, *gratis*. Participants will be paid in cash upon discharge from each session, with an escalating payment schedule used to encourage retention. Subjects will be compensated \$25 for the screening interview, \$125 for the first rTMS/Alcohol session, and \$175 for the second rTMS/Alcohol session. Subjects that complete only a portion of any study procedure will be compensated at a rate of \$15 per hour at the discretion of the study physicians.

Alcohol consumption follow-up

Subjects will be contacted and compensated \$25 four weeks after Session 2 for a timeline follow-back assessment of drinking⁴⁹.

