12.0 Statistical Considerations

Analyses

Sample Size

We plan to consent and screen 30 subjects, enroll 20 subjects and anticipate a 30% drop out rate, yielding 14 completers. This is consistent with our previous clinical trial efforts, including a study of adjunct rTMS for cognitive impairment in first-episode psychosis³⁷.

Statistical and Power Analyses

We will conduct a Cox proportional hazards survival analysis, which will control for drinking intensity, to determine effect sizes for a subsequent, properly powered formal study of the effect of rTMS on rate control alcohol self-administration. A recent review reported Cohen's d from 0.05 to 4.42 of rTMS on craving and other substance use disorder related outcomes⁵⁰. Our previous alcohol self-administration work showed effect sizes from 0.49 to 1.31 depending on the phenotype. Thus, overall, we hope for an effect size of at least 0.5 across SA1 and SA2.

Finally, with consent, we are collecting blood samples to allow for the combination of data from this project with previously collected human samples; enabling future analysis of polygenic risk in the combined sample.

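### The rTMS/sham order is described as randomised in Sections 5.0, 6.0 and 7.0, yet Section 7.0 also lets study physicians assign it for balance or safety

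*Combined protocol and SAP*

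**What the plan says.** Three places describe a random order without qualification.

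- Section 5.0, Study Design: "Subjects will be randomized to undergo one session of rTMS or sham", with the opposite condition at the second session.
- Section 6.0, Enrollment/Randomization: eligible subjects are "enrolled at the discretion of the Principle investigator and randomly assigned to one of the two schedules (rTMS first, or Sham first").
- Section 7.0, rTMS Treatment: "Subjects will be assigned a sequence of blinded study conditions in randomized and counterbalanced fashion". The condition labels, such as A and B, are set "by a non-blinded staff member who is not directly involved with the research team".

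One place differs. Section 7.0, Recruitment and Screening, says that an enrolled subject is either randomised to a schedule or "assigned to one of the two schedules based on group enrollment balance or subject safety at the discretion of the study physicians".

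Enrolment is itself a judgement. The same part of Section 7.0 says that "the investigators will decide whether or not to enroll the subject in the study", and Section 12.0 states: "We plan to consent and screen 30 subjects, enroll 20 subjects and anticipate a 30% drop out rate, yielding 14 completers".

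**The concern.** The Recruitment and Screening text is a stated rule, so this is more than a missing detail. It names two grounds for setting the order, enrolment balance and safety, and leaves both to the physicians' discretion. The public text does not say what degree of imbalance or what safety finding triggers it, how many subjects it may cover, whether its use is recorded, or how such subjects are analysed.

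Two things are at stake. First, the description: a report calling the order randomised would not be accurate for every subject. Second, predictability: assigning for balance requires knowing how many subjects are already in each order, which makes the next order easier to foresee for anyone who has the totals and also has a say in enrolment. If staff see only the A and B labels, the totals point to A-first or B-first. They point to active-first only if the meaning of the labels is known.

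The safety ground raises a separate question of consistency. The documents do not explain how choosing an order for safety fits with random sequences of blinded conditions.

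**Working it through.** **1. Do the passages agree?** Sections 5.0 and 6.0 allow one mechanism, random assignment. The rTMS Treatment text also allows one, random with counterbalancing. The Recruitment and Screening text allows two, random or physician-assigned. Counterbalancing is compatible with a restricted random list, such as a blocked one. It does not describe a physician choosing a schedule, and it does not cover safety. The conflict therefore remains after the most favourable reading.

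**2. How many orders could be affected?** Inputs from Section 12.0: 20 enrolled, 30% dropout. The plan's own figure reproduces: 20 × (1 − 0.30) = 14 completers. With no limit stated, the number of physician-assigned orders lies between 0 and 20 of 20.

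**3. Can the bias be sized?** For completers, stable differences between subjects largely cancel, because each subject receives both conditions. For discretion over order to bias the contrast, the route must be used, its use must be related to the type of subject, and the period effect must differ between types of subject. The documents give none of these quantities, and if any one is absent this source of bias is zero. The scope for choosing who takes the next place is at most 30 − 20 = 10 candidates, and it is zero if all 10 are lost to ineligibility. The range therefore includes zero, and the documents give no basis for an upper figure on the scale of the primary outcome.

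**4. Is balance a reasonable aim?** Yes. Under simple 1:1 randomisation of 20 subjects (binomial, both tails), a split of 12:8 or worse has probability 0.50, and 14:6 or worse has probability 0.12.

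**5. Does a blocked list deliver balance?** Two blocks of 4 and two of 6 give 4 + 4 + 6 + 6 = 20 places and 2 + 2 + 3 + 3 = 10 in each order. The two orders are never more than 3 apart.

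**6. What does the list's benefit depend on?** Suppose someone knows the totals, always guesses the order that is behind, and guesses at random when they are level. In a block of size 2b the expected number of correct guesses is b + ½ × (4^b / C(2b, b) − 1).

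- Block of 4 (b = 2): 2 + ½ × (16/6 − 1) = 2.833 of 4, or 71%.
- Block of 6 (b = 3): 3 + ½ × (64/20 − 1) = 4.1 of 6, or 68%.
- Proposed list: (2 × 2.833 + 2 × 4.1) / 20 = 13.87 / 20, or 69%.

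The current balance route, if always used when the orders are unequal, gives the same sequences as blocks of 2: 1 + ½ × (4/2 − 1) = 1.5 of 2, or 75%. If it is used on half or a quarter of the unequal occasions, with a 50:50 assignment otherwise, simulation of 20 enrolments gives 66% and 59%. These use rates are assumptions. A list whose totals and blocks are concealed gives 50%. With totals known, the list is thus more predictable than half or quarter use of the current route. What the list offers is the removal of discretion, together with concealment.

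**The case against.** The case for leaving this alone is substantial. In a two-session crossover, order is not the treatment comparison, so discretion over order cannot confound rTMS with sham as it would in a parallel-group trial. The plan already announces counterbalancing, so a wish for balance is no surprise. Assigning to the smaller group depends on counts and not on the subject, and at full use it produces the same sequences as blocks of two. The 10 consented subjects who are not enrolled are most naturally an allowance for screening loss, which leaves little or no room to choose between candidates. Section 12.0 plans no comparison of follow-up drinking by order and does not say how single-session data from dropouts will be used, so those routes to bias are only possibilities. The trial is a pilot intended to yield effect sizes.

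All of this stands as an argument about consequence. None of it removes the contradiction: counterbalancing does not license physician choice, and the safety ground is outside it altogether.

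A reader might infer that physicians would steer particular subjects into one order, or that the primary contrast is materially biased. The documents show no motive to steer and no period effect, so they do not support this. A reader might also infer that the safety route means the physicians know which schedule starts with active stimulation. The text does not say so; it simply leaves the point unexplained.

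**Conclusion.** The concern holds as a contradiction about how order is assigned, and confidence in that is high. It does not hold as a demonstrated bias. The effect on the primary contrast is likely to be small, cannot be quantified from the documents, and may be zero. That judgement rests on completers receiving both conditions, on the absence of any stated period effect, and on the unknown use of the discretionary route.

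Nor do the documents support saying that the trial is not randomised: the text permits exceptions without showing that any would occur. Severity is minor to should-fix. The reason to act is that the allocation statement should be true for every subject, and that balance can be had without discretion.

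Whether the Cox model in Section 12.0 should carry a period term is a separate question. Completers can be unequal by order under perfect randomisation, so the discretionary route is not its cause.

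**What to change.** 1. Delete the discretionary balance route from Section 7.0, Recruitment and Screening.
2. Assign every order from a pre-generated, concealed, blocked list, for example two blocks of 4 and two of 6 in random order. The non-blinded staff member outside the team, already provided for under rTMS Treatment, can hold it.
3. Withhold block sizes and running totals by order from those who decide enrolment. Without this step the list gains little.
4. Reconcile the safety route with the randomisation and blinding statements in Sections 5.0, 6.0 and 7.0, so that all four places describe the same process. The clinical content of that reconciliation is for the investigators.
5. Record any subject whose order was not taken from the list, and report a sensitivity analysis without those subjects.

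The cost is a short amendment and one list, with no new staff. Physicians lose the option to choose order for balance, which blocking supplies. Exact 10:10 balance applies to the 20 enrolled and is not guaranteed among the 14 expected completers.

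### The treatment order is assigned before the subject has agreed to book and before the Session 1 checks, so the counterbalance may not hold among those actually stimulated

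*Combined protocol and SAP*

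**What the plan says.** Section 6.0 (Enrollment/Randomization) assigns the order together with enrolment, once the eligibility criteria are met.

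Section 7.0 (Recruitment and Screening) gives the sequence in more detail. The investigators decide on enrolment from the screening interview. For enrolled subjects, "they will be either randomly assigned to one of the two schedules, or assigned to one of the two schedules based on group enrollment balance". Safety is named as a further ground for choosing the order. Contact for booking comes after this assignment: "at the discretion of the study physicians, and contacted to schedule their experimental sessions". The next sentence is conditional: "If the subject agrees to enroll in the study and schedules their study visits, they will be sent an email with pertinent information".

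The same section then describes the testing day, which begins with a physical examination and "testing of urine for hCG in females and a drug screen for all subjects, and documentation of zero BrAC before a 550 cal breakfast". Exclusion 8 in section 4.0 makes a positive breath-alcohol reading at the start of any session an exclusion.

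Under rTMS Treatment, section 7.0 states: "Subjects will be assigned a sequence of blinded study conditions in randomized and counterbalanced fashion". No allocation ratio, block size or replacement rule is given.

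Section 12.0 gives the numbers: "We plan to consent and screen 30 subjects, enroll 20 subjects and anticipate a 30% drop out rate, yielding 14 completers". The primary analysis is a Cox model that controls for drinking intensity; no period or sequence term is named.

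**The concern.** In a two-session crossover, equal numbers in the two orders make a shift from Session 1 to Session 2 cancel out of the rTMS–sham contrast. Such a shift is plausible here, for example through familiarity with the infusion task or the rate dial. The balance that matters is the one among subjects who receive the sessions. The plan fixes the order while a subject can still decline to book, fail to attend or fail a check that morning. Exclusion 8 cannot be fully assessed until the session starts, so the order is assigned before eligibility is complete.

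If such losses fall unevenly and are not made good, the orders among stimulated subjects become unequal. With no period term in the stated model, part of any period effect then enters the estimate. That estimate is the product of this pilot, since it is meant to inform a later powered study.

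**Working it through.** **Inputs.** From section 12.0: 20 enrolled, 30% dropout, 14 completers. Assumptions, because the documents are silent: 10:10 assignment, losses at random with respect to order, no replacement. Let k be the number of losses that occur before first stimulation; k is not stated, so its range is shown.

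**The plan's own figure.** 20 × (1 − 0.30) = 14, so 6 losses. This reproduces.

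**Completers under the current timing.** With 14 of 20 retained, P(a : 14 − a) = C(10,a) × C(10,14 − a) / C(20,14), where C(20,14) = 38,760.

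- 7:7: 120² / 38,760 = 14,400 / 38,760 = 0.372
- 8:6 either way: 2 × 45 × 210 / 38,760 = 0.488
- 9:5 or worse: (2 × 10 × 252 + 2 × 1 × 210) / 38,760 = 5,460 / 38,760 = 0.141

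These cover all six losses, whenever they occur. They do not isolate the effect of early assignment.

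**Stimulated subjects under the current timing.** Counting pre-stimulation losses only:

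- k = 2: 9:9 with probability 10² / C(20,2) = 100 / 190 = 0.53
- k = 4: 8:8 with probability 45² / C(20,4) = 2,025 / 4,845 = 0.42; a difference of 4 with probability 2 × 210 / 4,845 = 0.09

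**Completers if the order is assigned after the Session 1 checks.** Then 20 − k subjects are assigned as evenly as possible, and 6 − k are lost afterwards.

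| k | Assigned | Lost later | P(7:7) | P(9:5 or worse) |
|---|---|---|---|---|
| 0 | 10:10 | 6 | 0.37 | 0.14 |
| 2 | 9:9 | 4 | 36² / 3,060 = 0.42 | 2 × 126 / 3,060 = 0.08 |
| 4 | 8:8 | 2 | 8² / 120 = 0.53 | 0 |
| 6 | 7:7 | 0 | 1 | 0 |

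Odd k gives the same P(7:7) as the even value below it. For no k is late assignment worse.

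**Cost of an unequal split.** Let τ be the treatment effect and π the Session 2 minus Session 1 shift. The rTMS − sham difference is τ − π in the rTMS-first order and τ + π in the sham-first order. Averaged over subjects, the share of π left in the estimate is |n1 − n2| / n. If a period term is fitted, that share is removed and the variance rises by the factor n² / (4·n1·n2).

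| Split | Share of period effect, unadjusted | Variance factor with period term |
|---|---|---|
| 8:6 | 2/14 = 14% | 196/192 = 1.02 |
| 9:5 | 4/14 = 29% | 196/180 = 1.09 |
| 10:4 | 6/14 = 43% | 196/160 = 1.23 |

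These are for a simple paired contrast. They indicate the scale for the planned Cox model and are not exact for it.

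**The case against.** A reader might infer that each subject lost before Session 1 uses up one of 20 fixed allocations, and that the counterbalance is therefore broken. The documents do not support that. They describe no fixed list and no 10:10 ratio, and they do not say whether a lost subject's order is spent, reissued or replaced. Exact balance can also survive by chance: under the assumptions above, 7:7 or 8:6 together have probability 0.372 + 0.488 = 0.86.

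Other points deserve weight:

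- The plan has a balancing route, since physicians may assign by group enrolment balance. It could offset an imbalance, but it counts enrolled rather than stimulated subjects and works by discretionary, non-random assignment.
- Pregnancy, drug and breath-alcohol tests are also listed as screening tools (though the Study Calendar marks breath alcohol only at the experimental visits). A positive drug screen excludes only on physician judgement, and the plan does not say whether a failed check means rescheduling or removal. So few subjects may be lost at this step.
- The payment rises from $125 to $175 to encourage retention, which suggests that loss between sessions was expected. Late assignment cannot prevent that.
- Under random loss, neither order is favoured in expectation, and a period term makes an 8:6 split cheap (variance factor 1.02).
- A replacement rule is an alternative remedy, and this is a pilot.

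These points limit the size of the problem. They do not remove it: the stated sequence assigns early, no rule covers the gap, and no period term is named. The one reason in the text for choosing an order in advance is the physicians' safety discretion, which applies to individual subjects and does not require everyone to be assigned early.

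**Conclusion.** The point holds in a limited form. Assignment precedes both the subject's agreement to book and the Session 1 checks, and nothing says what happens to subjects lost in between. The counterbalance promised under rTMS Treatment is therefore not secured among those stimulated. Whether it fails depends on k, which the documents do not give. The gain from late assignment runs from nothing (k = 0, P(7:7) stays at 0.37) through 0.42 (k = 2) and 0.53 (k = 4) to certainty (k = 6).

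This rests on 10:10 assignment, random loss and no replacement. Random loss is reasonable before Session 1, because blinded subjects have not yet received either condition; it is less secure between sessions. The 14% and 29% are shares of a period effect whose size is unknown, in an unadjusted paired contrast. The point merits a change because the remedy is nearly free, not because a large bias has been shown.

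**What to change.** 1. In 6.0 and 7.0, assign the order at Session 1, after the subject has attended and passed that morning's checks and before stimulation. Take the next entry from a pre-generated counterbalanced list, for example sealed or coded entries prepared by the non-blinded staff member who labels the conditions. Generate the list so that it stays near balance wherever it stops (small blocks, with the size not disclosed to the blinded team), because the number reaching Session 1 is not known in advance.
2. Drop assignment by enrolment balance, which the list makes unnecessary. The safety route is a clinical matter outside this point; reconcile its wording with 6.0 and with rTMS Treatment, and identify in the data any subject assigned by it.
3. In 12.0, add a period term to the Cox model. This covers imbalance from losses between sessions, which later assignment cannot prevent.
4. Keep the 30/20/14 figures as they are. Redefining enrolled as assigned at Session 1 would shift them.

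**Cost.** Wording in 6.0, 7.0 and 12.0, and one extra model parameter. The list must be accessible on testing mornings. The documents do not say that the non-blinded staff member is available then, which is why entries prepared in advance are suggested.
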